We are using a dose within the higher range that has shown to be safe and efficacious in clinical studies. We do not have human T reg efficacy data: therefore as this is an exploratory study, this is scientifically a good dose to use. We would therefore not up-titrate from this dose. We are working on the hypothesis that the pharmacodynamic effect of AZD1656 on Treg migration activity is the same as for glucose lowering (we have no evidence to suggest this is not correct), and we proposed using what we know is an effective and safe dose in order to adequately test the hypothesis. We have chosen not to start at and lower dose and subsequently up-titrate the dose: given the proposed mechanism of action of AZD1656, early mobilisation of regulatory T cells with subsequent amelioration of renal ischaemia-reperfusion injury is required in order to benefit the new transplant. We are measuring delayed graft function as one of the secondary clinical endpoints as a surrogate for improved renal outcome within the first 7 days.

From a safety perspective, all of the patients will be diabetic and induction therapy given for renal transplantation is associated with hyperglycaemia; in addition as the patients are inpatients for the first 5-7 days post transplant (and during initiation of study drug) they are closely monitored for hypoglycaemia. The risk of hypoglycaemia after this period is low based on the data from the previous Phase 2 diabetes studies with AZD1656. If recurrent hypoglycaemia occurs despite removal of other anti-diabetic medications, then the study medication will be withdrawn as per withdrawal criteria.

Preclinical & Clinical Data

Investigator's Brochure AZD1656, Edition 9, September 2020

Twenty-five clinical studies have been completed to evaluate the safety, tolerability, PK, PD and drug interactions with AZD1656. Approximately 960 subjects have been exposed to AZD1656 for up to 6 months' duration. In patients with type 2 diabetes and renal impairment, the PK and PD effects after single doses of AZD1656 were comparable to diabetic patients with normal renal function.

Across clinical studies, AZD1656 has been well tolerated and no safety concerns have been raised. No safety signals have been identified regarding vital signs, ECG, weight, BMI and physical findings.

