All patients will be seen frequently in a specialist post-transplant clinic where, as part of their standard of care, they will have their blood glucose measured regularly along with makers of diabetic control including HbA1c. The patient will be given instructions to measure blood glucose if they get symptoms of hyperglycaemia (e.g. thirst, polyuria) or hypoglycaemia (cold sweat, dizziness). If a major hypoglycaemic event occurs, or more than one minor event since last visit, the patient will be told to contact the investigator before the next visit.

As with all patients with diabetes post-transplant, if a patient's blood glucose control is considered by their clinical team to be too high or low, then their regular antidiabetic medications will be altered to achieve diabetic control targets as per our

standard of clinical care. National guidelines in the management of CKD patients with diabetes suggest controlling the HbA1c to between 6.5% (48mmol/mol) to 8.5% (68mmol/mol). Within this range there are suggestions to aim for tighter control (towards 6.5%) or less tight control (towards 8.5%) on an individualised patient basis (Renal Association 2018).

Reproductive restrictions

Female study participants

Women of child-bearing potential are permitted to participate in this study provided that they agree to avoid pregnancy through the use of a highly effective form of contraception starting from the time of study enrolment until the final safety follow-up visit has been completed (2 weeks after cessation of study medication). AZD1656 has low potential for drug-drug interaction through induction of any of the CYP enzymes so an interaction with hormonal contraception is not anticipated. Methods of highly effective contraception are outlined in section 12.2 (Exclusion criteria). If a female participant should become pregnant, then the study medication will be stopped. She will be asked to consent to the collection of data about her pregnancy, and the birth and health of her baby.

Male study participants

It is important that women of childbearing potential, who are the partners of male patients, do not become pregnant during the study and until the participant has completed the safety follow up visit.

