13.7.2 Trial assessments

Screening visit

Informed consent Inclusion/exclusion criteria

Documentation of a negative pregnancy test from pre-transplant care

In women of childbearing potential: defined as women following menarche until becoming post-menopausal, unless permanently sterile. Permanent sterilisation methods include hysterectomy, bilateral salpingectomy and bilateral oophorectomy. A postmenopausal state is defined as the absence of menses for 12 months without an alternative medical cause.

Medical history

Demographic data

Concomitant medication

Visit 1 - to occur within 24 hours post-transplant

Inclusion/exclusion criteria

Transplant data

Documentation of a negative pregnancy test

Concomitant medication

Targeted physical examination

Adverse event reporting

Laboratory bloods: including fasting c-peptide, cholesterol and serum glucose; serum urea and electrolytes (including creatinine), albumin, alkaline phosphatase (ALP), bilirubin, alanine aminotransferase (ALT), bone profile and C-reactive protein; haemoglobin and HbA1c; and serum save. Results from bloods that have been taken as part of routine care may also be included on the case record forms.

20ml of blood will also be taken for peripheral Treg quantification.

Vital signs recording

Weight

Randomisation

Study drug dispense

In addition, the renal biopsy specimen collected as per clinical care at time of biopsy will be stained for Treg cell markers.

Visit 2 (1 week post randomisation +/- 3 days))

Check drug adherence Concomitant medication Documentation of a negative pregnancy test Targeted physical examination Weight Vital signs recording

Fasting blood tests: including fasting c-peptide, cholesterol and serum glucose; serum urea and electrolytes (including creatinine), albumin, alkaline phosphatase (ALP), bilirubin, alanine aminotransferase (ALT), bone profile and C-reactive protein; haemoglobin and HbA1c and serum save. Results from bloods that have been taken as part of routine care may also be included on the case record forms. 20ml of blood will also be taken for peripheral Treg quantification.

Adverse event reporting

Visit 3 (2 weeks post randomisation +/- 3 days)

Activities as per visit 2 with exception of blood collection for Treg quantification

Visit 4 (4 weeks post randomisation +/- 3 days)

Activities as per visit 3

Visit 5 (8 weeks post randomisation +/- 1 week)

Activities as per visit 3

Visit 6 (12 week post randomisation +/- 1 week)

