13.8 Withdrawal criteria

Study medication will be stopped in the following situations:

- 1. Hypoglycaemia despite removal of other glucose-lowering drugs: e.g. repeated events of minor hypoglycaemia defined as:
 - An episode with symptoms and confirmed low glucose (<3.9 mmol/L).
 - An episode with low glucose (<3.9 mmol/L).

- An episode with symptoms suggestive of hypoglycaemia when glucose was not measured.

If a patient has episodes of hypoglycaemia, their anti-diabetic medications will be altered as per standard of clinical care.

2. One event of major hypoglycaemia regardless of any other diabetes drugs, as defined by the American Diabetes Association (ADA):

- Requires assistance of another person to actively administer carbohydrates, glucagon, or take other corrective actions.

Plasma glucose concentrations may not be available during an event, but neurological recovery following the return of plasma glucose to normal is considered sufficient evidence that the event was induced by a low plasma glucose level

- 3. Impaired hepatic function (AST/ALT >x3 ULN,) due to the hepatic metabolism of AZD1656
- 4. The patient's target HbA1c is less than 6.5% and their other anti-diabetic medications have been withdrawn.

If any of these situations occur, the subject will be withdrawn from the study medication, but will continue in the study with other study related activities.

If the patient's clinical care team feel that the patient requires treatment with gemfibrozil, then the patient will be withdrawn from the study medication, but continue other study related activities. This is not expected to happen in practice as gemfibrozil interacts with other immunosuppression medication the patient takes as part of their standard transplant regime, so gemfibrozil is avoided in transplantation medicine.

Patients may be withdrawn from the study if the investigator feels that individual adverse events or new information gained mean that it is not safe to continue the study, or if it is felt to be in the participant's best interest to stop the study.

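### Stopping criterion 4 tests the patient's target HbA1c, not the measured value, so it cannot trigger for any target in the cited 6.5–8.5% range

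*Combined protocol and SAP*

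**What the plan says.** Protocol section 13.8 sets out the situations that end study medication. Criteria 1 and 2 concern hypoglycaemia and criterion 3 concerns liver enzymes. Criterion 4 is: "The patient's target HbA1c is less than 6.5% and their other anti-diabetic medications have been withdrawn". The consequence is not optional: "If any of these situations occur, the subject will be withdrawn from the study medication". The patient then stays in follow-up.

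Section 9.2 shows what the protocol means by a target. If the clinical team judges control too high or too low, "their regular antidiabetic medications will be altered to achieve diabetic control targets". National guidelines are said to "suggest controlling the HbA1c to between 6.5% (48mmol/mol) to 8.5% (68mmol/mol", and individual goals are chosen inside that interval: "Within this range there are suggestions to aim for tighter control (towards 6.5%) or less tight control (towards 8.5%) on an individualised patient basis".

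Measured HbA1c is handled separately. In clinic, "they will have their blood glucose measured regularly along with makers of diabetic control including HbA1c". It is also among the laboratory bloods in sections 13.7.1 and 13.7.2.

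No other section restates criterion 4 using a measured value. Section 9.2 repeats only the hypoglycaemia rule: "If recurrent hypoglycaemia occurs despite removal of other anti-diabetic medications, then the study medication will be withdrawn as per withdrawal criteria". Section 15.15 gives the investigator only a general discretion to stop the drug.

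**The concern.** Criterion 4 appears meant for a patient whose HbA1c has fallen below the range when no other glucose-lowering drug is left to reduce. Section 15.15 allows no dose change, so stopping study drug is then the only remaining adjustment to glucose-lowering treatment. As worded, the rule does not respond to that situation, because it asks what goal was set and not what was measured.

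It can also misfire the other way. A patient given a target below 6.5% whose other drugs had been withdrawn would have to stop study drug even with a high HbA1c.

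At stake is the reliability of one mandatory safety rule. Criterion 1 depends on low glucose being noticed. Section 9.2 tells patients to test when they have symptoms, yet it also reports that some low values on AZD1656 were asymptomatic and found only at scheduled measurement. An HbA1c rule could act as a backstop for such cases. Sample size, significance level and the primary analysis are not in question.

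**Working it through.** There is no figure in the plan to reproduce. The check applies the rule as written and compares it with a rule based on the measured value.

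**Inputs**
- Rule as written (section 13.8): stop if target < 6.5% and other anti-diabetic drugs are withdrawn.
- Measured-value rule: stop if measured HbA1c < 6.5% and other anti-diabetic drugs are withdrawn.
- Cited target range (section 9.2): 6.5% to 8.5%.
- Measured HbA1c from 4.0% to 12.0%: an assumed grid, because the documents give no HbA1c distribution.

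**Step 1: the boundary.** The lowest target in the range is 6.5%. The condition 6.5 < 6.5 is false, so it is false for every higher target too.

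**Step 2: full grid.** Targets 6.5–8.5% in steps of 0.1 give 21 values. Measured values 4.0–12.0% in steps of 0.1 give 81. Other drugs withdrawn or not gives 2. Total: 21 × 81 × 2 = 3,402 combinations.
- Rule as written: triggers in 0 of 3,402.
- Measured-value rule: triggers in 21 × 25 × 1 = 525 (25 measured values, 4.0–6.4%, with other drugs withdrawn). This shows only that the rule becomes operative; it is not a probability.
- With target and withdrawal status held fixed, changing the measured HbA1c never changed the result of the rule as written. This was also true at targets of 6.0% and 6.4%.

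**Step 3: illustrative patients, other drugs withdrawn**

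| Target | Measured HbA1c | As written | Measured < 6.5% | Measured < own target |
|---|---|---|---|---|
| 6.5% | 5.5% | continue | stop | stop |
| 7.0% | 5.5% | continue | stop | stop |
| 7.5% | 5.5% | continue | stop | stop |
| 8.5% | 5.5% | continue | stop | stop |
| 6.0% | 9.0% | stop | continue | continue |
| 7.5% | 6.8% | continue | continue | stop |

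The first four rows are the situation the rule seems meant for, and it is silent in all four. The fifth is the misfire. The last shows that the two plausible intentions can disagree, so the reader cannot simply infer the right one.

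**Step 4: exposure lost if a measured-value rule stops a patient.** Planned treatment is 12 weeks. A stop at visit 2, 3, 4 or 5 (week 1, 2, 4 or 8) forgoes 11/12 = 92%, 10/12 = 83%, 8/12 = 67% or 4/12 = 33%.

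**Step 5: dilution of the ITT difference.** Assume k of the 25 AZD1656 patients stop and keep no drug effect at month 3, a worst case. The difference then shrinks by k/25: 4%, 8% and 12% for k = 1, 2 and 3. These k are assumed, not estimated.

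**The case against.** The strongest reply accepts the wording but disputes its weight.

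- **Other protection exists.** Criterion 1 counts repeated glucose readings below 3.9 mmol/L with or without symptoms, and criterion 2 acts on a single major event. Sections 13.8 and 15.15 let the investigator stop the drug on safety grounds. Section 9.2 describes 5–7 inpatient days, then clinic twice weekly for 6 weeks and weekly for 6 more. This stands: what is left is low HbA1c without qualifying hypoglycaemia and without clinician concern.
- **Local staff will read it sensibly.** There is one site (section 11.7), and the transplant team is to be educated on the protocol (section 17.4). This lowers the risk but does not remove it. The last row of the table shows two sensible readings giving different decisions, and section 22.5 does not permit planned deviations.
- **The range only advises.** A clinician may set a target below 6.5%, so the rule is not dead for every conceivable patient. This is correct, and the conclusion is limited to targets in the cited range. For a target below it, the rule still ignores the result.
- **Measured HbA1c may act indirectly**, by prompting withdrawal of the other drugs. This is also correct, but it bears only on the second condition, and the first stays unmet.
- **Any rewording guesses the intent and may cost exposure.** This is fair, so the threshold and the handling of patients already below it are put to the clinicians. The dilution figures rest on assumed counts and should carry little weight.

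**Conclusion.** The point holds. As written, criterion 4 contains no measured HbA1c and cannot be met for any target from 6.5% to 8.5%. That follows from the text alone and needs no assumption about patients. It is most likely a slip of wording, but it sits in a mandatory stopping rule and gives the wrong instruction if followed.

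The practical safety gap is modest. The number of patients affected cannot be computed: the documents give no HbA1c distribution, and sections 12.1 and 12.2 set no minimum HbA1c at entry. The sponsor should correct it.

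**What to change.** Replace criterion 4 with a sentence such as: *Measured HbA1c on study treatment, from a scheduled or routine-care sample, is below 6.5% although the patient's other glucose-lowering drugs have been stopped.* The responsible clinicians should:

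1. Confirm that 6.5%, the protocol's own figure, is the intended threshold, and not the patient's individual target.
2. State whether the rule applies to a patient whose visit 1 HbA1c was already below 6.5%.

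The cost is one sentence in a protocol amendment. No test is added: HbA1c is in the study bloods from visit 1, and section 13.7.2 says of other results, "Results from bloods that have been taken as part of routine care may also be included on the case record forms". The drawback is that some patients may stop study drug earlier, possibly at week 1 if they entered with a low HbA1c. Decision 2 controls how often that happens.

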There have been no treatment related changes in safety laboratory variables including muscle biomarkers and liver function tests in Phase I to IIa. From the few cases with increased liver enzymes in Phase IIb, a minor increase from AZD1656 treatments could not be excluded.

AZD1656 is mainly metabolised via CYP2C8, therefore potent inhibitors of CYP2C8 (e.g. gemfibrozil) may increase exposure to this drug (AUC).

Other than inhibitors of CYP2C8, no significant drug-drug interactions have been reported in phase I/II clinical trials; however there may be drug-drug interactions that are as yet unknown.

Reproductive restrictions

No data is available on the effects of AZD1656 on pregnancy and lactation in humans. Preclinical studies have shown that AZD1656 is not genotoxic. There was no effect on male fertility in rat. Overall, the effects of AZD1656 on embryofoetal development seen in pre-clinical studies were considered to be secondary to maternal hypoglycaemia. Results from the preclinical repro-toxicity studies support inclusion of women of childbearing potential in clinical studies, provided that pregnancy is prevented using a highly effective form of contraception. In case of pregnancy during the study, treatment should be stopped.

How the risk will be minimised/managed

Hypoglycaemia:

As with most anti-diabetic medications there is a risk of hypoglycaemia. However, following a renal transplant, given the increased glucose production from the steroid medications along with increased insulin metabolism, hyperglycaemia rather than hypoglycaemia is more of an issue. For AZD1656, in phase I to IIa, few hypoglycaemic events have been reported and only rarely with a plasma glucose level below 3 mmol/L (54 mg/dL). In phase IIb, the proportion of patients reporting hypoglycaemic events was overall small. Fewer patients in the AZD1656 treatment groups reported hypoglycaemic events compared to the glipizide group. Low glucose levels were either asymptomatic (detected in scheduled measurement) or associated with mild symptoms, and in all cases manageable by the patients. All events with low plasma glucose have responded rapidly to carbohydrate intake.

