12.2 Exclusion Criteria

- a) Unable to consent
- b) Known allergy/intolerance to AZD1656
- c) Pregnant or breastfeeding women
- d) Planning on becoming pregnant/unwilling to use highly effective contraception* during the 3 month treatment period and for 2 weeks afterwards
 - a. In the case of men with sexual partners who are women of childbearing potential: refusal to wear a condom **and** female partner planning on becoming pregnant/unwilling to use highly effective contraception* during the 3 month treatment period and for 2 weeks afterwards
- e) Clinically significant history of abnormal physical and/or mental health as judged by the investigator other than conditions related to chronic kidney disease
- f) Current or planned use of strong inhibitors of CYP2C8
- g) Participation in an investigational drug trial in the 3 months prior to administration of the initial dose of study drug

*Highly effective contraception methods are defined as those that can achieve a failure rate of <1% per year when used correctly and consistently. These include:

- Combined (oestrogen and progestogen containing) hormonal contraception associated with inhibition of ovulation either oral, transvaginal or transdermal
- Progestogen-only hormonal contraception associated with inhibition of ovulation either oral, injectable or implantable
- Intrauterine device (IUD) or intrauterine hormone-releasing system (IUS)
- Bilateral tubal occlusion
- Vasectomised partner provided that the partner is the sole sexual partner of the participant and that the vasectomised partner has received medical assessment of surgical success

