15.17 Prior and Concomitant medication

Given the theoretical increase in AUC (but not C_{max}) with gemfibrozil. Any patient who is currently taking this agent will be excluded from the study.

Prior and Concomitant medication lists will be recorded in the case record forms

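### The mandatory on-treatment stop for CYP2C8 inhibition (13.8) covers gemfibrozil only, although exclusion (f) bars every strong CYP2C8 inhibitor at entry

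*Combined protocol and SAP*

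**What the plan says.** - **Section 9.2 (rationale).** CYP2C8 is the main metabolic route for AZD1656, so "potent inhibitors of CYP2C8 (e.g. gemfibrozil) may increase exposure to this drug (AUC"). The next statement is "Other than inhibitors of CYP2C8, no significant drug-drug interactions have been reported in phase I/II clinical trials", with the caveat that unknown interactions may exist.
- **Section 12.2, exclusion (f) (entry).** "Current or planned use of strong inhibitors of CYP2C8".
- **Section 13.8 (on treatment).** Four numbered criteria stop study drug: repeated minor hypoglycaemia after other glucose-lowering drugs are removed, one major hypoglycaemic event, AST/ALT above three times the upper limit of normal, and a target HbA1c below 6.5% with other anti-diabetic drugs already withdrawn. A separate paragraph deals with the interaction: if the clinical team feels the patient "requires treatment with gemfibrozil, then the patient will be withdrawn from the study medication, but continue other study related activities". It continues: "This is not expected to happen in practice as gemfibrozil interacts with other immunosuppression medication".
- **Section 15.15.** Dose changes are not permitted. The investigator may stop study drug on safety grounds.
- **Section 15.16.** Interaction data are given for gemfibrozil only.
- **Section 15.17.** On gemfibrozil: "Any patient who is currently taking this agent will be excluded from the study". Concomitant medication is recorded in the case record form, and no action is attached to the record.

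**The concern.** The entry rule and the on-treatment rule address the same hazard but have different scope. At entry the whole class of strong inhibitors is barred. After randomisation only one member of the class forces a stop, and it is the member the protocol does not expect to see used.

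Followed as written, the plan allows a patient to stay on full-dose AZD1656 after starting a drug that would have kept that patient out of the trial a few weeks earlier. The dose cannot be reduced, so the only choice is to continue or stop, and no rule tells the investigator which. Two patients in the same position could be handled differently. What is at stake is participant safety and consistent conduct, not the validity of the primary comparison.

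**Working it through.** The plan has no figure of its own to reproduce on this point. The check is a comparison of sections, followed by what little can be counted.

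**1. Scope of each rule**

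| Section | When it applies | Drugs covered | Mandatory? |
|---|---|---|---|
| 9.2 | Rationale | CYP2C8 inhibitors; gemfibrozil as an example | – |
| 12.2 (f) | Entry | All strong CYP2C8 inhibitors, current or planned | Yes |
| 15.17 | Entry | Gemfibrozil | Yes |
| 13.8, interaction paragraph | On treatment | Gemfibrozil | Yes |
| 13.8, general withdrawal paragraph | On treatment | Not tied to any drug | No (may) |
| 15.15 | On treatment | Not tied to any drug | No (may) |

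No section supplies a mandatory on-treatment rule for the other strong inhibitors. Exclusion (f) reaches planned use, but it is applied at entry and cannot govern a start that nobody had planned.

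**2. Whether the numbered criteria in 13.8 fill the gap**

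They do not. The two hypoglycaemia criteria and the HbA1c criterion respond to glycaemia. The AST/ALT criterion is justified as "due to the hepatic metabolism of AZD1656", but it is triggered by raised enzymes, not by a co-prescription. After hypoglycaemic episodes, "their anti-diabetic medications will be altered as per standard of clinical care", which is again a response to an effect. The gemfibrozil rule is the only one that acts before an effect appears.

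**3. Size of the interaction**

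For gemfibrozil, 15.16 reports:
- a 2.7-fold AUC after a single dose;
- about 50% predicted accumulation on twice-daily dosing;
- no statistically significant Cmax rise;
- a reduced level of the active metabolite.

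No figure is given for any other inhibitor.

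For scale, assume that exposure is proportional to dose. One 100 mg dose then corresponds to 2.7 × 100 = 270 mg, below the 450 mg single dose already given to patients (9.1). The daily dose of 2 × 100 = 200 mg corresponds to 2.7 × 200 = 540 mg/day, against a studied repeated-dose range of 10 to 200 mg daily (9.1).

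**4. How soon a new drug would be noticed**

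On-treatment medication checks fall at weeks 1, 2, 4, 8 and 12 (13.7.2).
- Visit 5 is day 56 ± 7 (49 to 63) and visit 6 is day 84 ± 7 (77 to 91). The planned gap is 84 − 56 = 28 days; the longest is 91 − 49 = 42 days.
- Visit 4 is day 28 ± 3, so the longest gap from visit 4 to visit 5 is 63 − 25 = 38 days.
- Standard clinic attendance (9.2) is 2 × 6 + 1 × 6 = 18 contacts in 12 weeks, slightly fewer because the first 5 to 7 days are inpatient. Source records are reviewed at least monthly (17.4).

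These intervals describe the setting. They do not measure the missing rule, and rewording 13.8 would not shorten them.

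**5. Number of patients**

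The documents give no frequency of unplanned starts. Assuming 0% to 5%:
- overall: 50 × 0 = 0 to 50 × 0.05 = 2.5 patients;
- on AZD1656: 25 × 0 = 0 to 25 × 0.05 = 1.25 patients.

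**The case against.** The strongest reply is that the gap is one of drafting and that patients are well protected without the extra words. The investigator can stop study drug prospectively under 15.15, or withdraw a patient in that patient's best interest under 13.8, without waiting for hypoglycaemia or an enzyme rise. An investigator who has just applied exclusion (f) knows about the interaction. Planned use is already screened out, the transplant team is to be trained on the protocol, and clinic contact is frequent. ALT and HbA1c are measured at each study visit. The documents name no other strong CYP2C8 inhibitor, give no data on one, and do not suggest that one is used in this population. Even with gemfibrozil the Cmax did not rise significantly and the active metabolite fell, and nothing in the documents shows harm.

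Much of this stands. It is why the point is minor and why its frequency has to be left as an assumption. It does not close the gap. Discretion was available for gemfibrozil too, yet the sponsor chose a mandatory stop there, and the documents give no reason to treat the rest of the class differently. The reassurance about non-use in transplantation is specific to gemfibrozil. The single-dose comparison is comforting, but on repeated dosing the implied exposure would lie above the studied range.

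**Conclusion.** The concern holds. The protocol describes a class interaction and bars the class at entry, but after randomisation it makes stopping mandatory for gemfibrozil alone. An unplanned start of another strong CYP2C8 inhibitor leads only to a discretionary stop, or to a stop once an effect has appeared.

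Severity is minor. The existing safeguards limit the consequence, and the ITT primary comparison in 19.5 is unaffected. The textual finding rests on no assumption. The 0 to 2.5 patients of 50 rests entirely on an assumed 0% to 5% start frequency and is not evidence of how large the risk is. The exposure equivalents assume dose proportionality and apply to gemfibrozil only.

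**What to change.** In 13.8, replace the trigger *gemfibrozil* with *gemfibrozil or any other strong CYP2C8 inhibitor*, keeping the same action: stop study drug and continue all other study activities. In 15.17, state that strong CYP2C8 inhibitors, including gemfibrozil, must be neither in use at entry nor started during the 3-month treatment period, and that study drug stops under 13.8 if one becomes clinically necessary. A reference defining which inhibitors count as strong would help staff, but it is a separate convenience; exclusion (f) already calls for that judgement.

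The cost is a few words in 13.8 and a sentence or two in 15.17. No new data are needed, because concomitant medication is already recorded at every study visit. The downside is that an occasional patient stops study drug early: 0 to 2.5 of 50 across both arms under the assumed range. Such a patient stays in follow-up and in the ITT analysis.
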